- *Are at risk for economic, social, or legal consequences from the study (e.g., individuals who would have to answer study survey questions about their drug use or HIV status).*

Indicate specifically whether you will include or exclude each of the following special populations:

- Adults unable to consent-EXCLUDED
- Individuals who are not yet adults (infants, children, teenagers)-EXCLUDED
- Pregnant women-EXCLUDED
- Prisoners-EXCLUDED

(You may not include members of the above populations as subjects in your research unless you indicate this in your inclusion criteria.)

If the Human Research involves cognitively impaired adults, review the “CHECKLIST: Criteria for Research Involving Cognitively Impaired Adults” to ensure that you have provided sufficient information.

PROTOCOL TITLE: *Tolerability, Safety, and Efficacy of Tedizolid as Oral Treatment for Bone and Joint Infection*

Revised: 8/10/18 Version 1.6

If the Human Research involves persons who have not attained the legal age for consent to treatments or procedures involved in the research (“children”), review the “CHECKLIST: Criteria for Research Involving Children” to ensure that you have provided sufficient information.

If the Human Research involves pregnant women, review the “CHECKLIST: Criteria for Research Involving Pregnant Women” to ensure that you have provided sufficient information.

If the Human Research involves neonates of uncertain viability or non-viable neonates, review the “CHECKLIST: Criteria for Research Involving Neonates” to ensure that you have provided sufficient information.

18) Drugs or Devices

If the Human Research involves drugs or device, describe your plans to store, handle, and administer those drugs or devices so that they will be used only on subjects and be used only by authorized investigators.

Tedizolid 200 mg oral tablets will be stored at and dispensed by the LA BioMed Investigational Drug Service (IDS) by trained pharmacists to the study team member who will then provide to the subjects. The IDS will maintain a drug dispensation log and provide to the investigator at the end of the study.

Because this study is using tedizolid for longer than the FDA approved duration, we have received an IND (133495) which was approved to proceed on 1/12/17. The study drug will be prescribed/administered as prolonged antibiotic therapy for a duration of time based on the judgment of the primary/consulting physician who is treating the subject's bone and joint infection.

19) Multi-Site Human Research*

Not Applicable – not a multi-site study.

If this is a multi-site study where you are the lead investigator, describe the processes to ensure communication among sites, such as:

- *All sites have the most current version of the protocol, consent document, and HIPAA authorization.*
- *All required approvals have been obtained at each site (including approval by the site's HSC of record).*
- *All modifications have been communicated to sites, and approved (including approval by the site's HSC of record) before the modification is implemented.*
- *All engaged participating sites will safeguard data as required by local information security policies.*
- *All local site investigators conduct the study appropriately.*
- *All non-compliance with the study protocol or applicable requirements will be reported in accordance with local policy.*

Describe the method for communicating to engaged participating sites:

PROTOCOL TITLE: *Tolerability, Safety, and Efficacy of Tedizolid as Oral Treatment for Bone and Joint Infection*

Revised: 8/10/18 Version 1.6

- *Problems.*
- *Interim results.*
- *The closure of a study*

20) Community-Based Participatory Research

Describe involvement of the community in the design and conduct of the research.

Note: “Community-based Participatory Research” is a collaborative approach to research that equitably involves all partners in the research process and recognizes the unique strengths that each brings. Community-based Participatory Research begins with a research topic of importance to the community, has the aim of combining knowledge with action and achieving social change to improve health outcomes and eliminate health disparities.

Not Applicable

21) Sharing of Results with Subjects

Describe whether results (study results or individual subject results, such as results of investigational diagnostic tests, genetic tests, or incidental findings) will be shared with subjects or others (e.g., the subject’s primary care physicians) and if so, describe how it will be shared.

Any clinically significant (as determined by [name] or [name]) lab, culture, or survey results (See Data Collection Fields, V1.0 for a complete list) or other incidental findings will be shared with the subject and their primary care providers if clinically indicated.

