- f) Severe hepatic dysfunction as defined by liver function tests (ALT, ALP, AST, total bilirubin) \geq 3.0 times the upper limit of normal. as determined by the following limits from a baseline CMP obtained within the past 7 days. If a CMP has not been performed within the past 7 days, baseline levels may be used from a CMP performed within the past 2 months as long as another CMP is performed on the day of enrollment and the subject's levels are within the following limits.
- g) Hypersensitivity to tedizolid or other oxazolidinone-class antibiotics or similar compounds.
- h) Ongoing antibiotic-associated colitis.
- i) A diet high in tyramine-containing foods such as pickled or fermented meats and cheeses, wine, or avocados per investigator discretion.
- j) Concurrent use of sodium picosulfate (brand names: Sodipic Picofast, Laxoberal, Laxoberon, Purg-Odan, Picolax, Guttalax, Namilax, Pico-Salax and Prepopik).
- k) Concurrent use of any monoamine oxidase inhibitors (MAOIs) or use of MAOIs within two weeks of starting the study medication.
- l) Previous participation in the study.
- m) Use of tedizolid for any condition in the past 3 months.

PROTOCOL TITLE: *Tolerability, Safety, and Efficacy of Tedizolid as Oral Treatment for Bone and Joint Infection*

Revised: 8/10/18 Version 1.6

n) Any other medical, psychological, or social condition that, in the opinion of the Investigator, would prevent the patient from fully participating in the study or would represent a concern for study compliance or constitute a safety concern to the patient.

c) Local Number of Subjects

Indicate the total number of subjects to be accrued locally.

We will enroll subjects until we obtain 50 subjects who are analyzable and have completed all follow-ups through 12 weeks. The attrition rate for this study is unclear but we estimate a possible attrition rate of 10%, which would require enrollment of approximately 55 subjects.

If applicable, distinguish between the number of subjects who are expected to be enrolled and screen, and the number of subjects needed to complete the research procedures (i.e., numbers of subjects excluding screen failures.)

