We anticipate enrolling approximately 55 patients as we anticipate an approximate 10% attrition rate in order to have study outcomes for 50 subjects in total. However, the attrition rate for a study of this length is unclear and we may need to enroll a different number of subjects to achieve our analyzable population of 50 subjects.

d) Study-Wide Number of Subjects*

If this is a multicenter study, indicate the total number of subjects to be accrued across all sites.

This is the only enrollment site.

e) Study Timelines*

Describe:

- *The duration of an individual subject's participation in the study.*

Approximately 12 weeks of in person follow up visits, with a final phone call three months after completion of antibiotic treatment. Thus, the total duration of an individual subject will range from 16 weeks to 24 weeks.

- *The duration anticipated to enroll all study subjects.*

Approximately 16 months.

- *The estimated date for the investigators to complete this study (complete primary analyses)*

Approximately 2 years.

f) Study Endpoints*

Describe the primary and secondary study endpoints. Describe any primary or secondary safety endpoints.

PROTOCOL TITLE: *Tolerability, Safety, and Efficacy of Tedizolid as Oral Treatment for Bone and Joint Infection*

Revised: 8/10/18 Version 1.6

The primary study endpoint is the tolerability of prolonged (≥ 4 weeks) courses of tedizolid antibiotic therapy for patients with bone and joint infection. CBC and a CMP (comprehensive chemistry panel including liver function tests) will be performed at the following intervals after initiation of tedizolid. We will administer standardized surveys about drug side effects and tolerability at all follow-up visits (weeks 1, 2, 3, 4, 5, 6 (optional), 7 (optional), 8 (optional), 9 (optional), 10 (optional), 11 (optional), 12). Adverse events will be measured using the Medical Dictionary for Regulatory Activities Terminology (MedDRA) version 18.1 (or the most current version).

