Once informed consent is obtained, we will collect data on all subjects' demographics, co-morbidities, surgical history, pertinent microbiology results, and all concomitant medications using standardized forms. For exclusion criteria e) and f) regarding cytopenias and liver function, CBC/CMPs from the past 14 days will be evaluated through a medical chart review. Note that if a CBC has not been performed within the past 14 days, a CBC will be performed on the day of enrollment prior to any study drug being administered to ensure the patient does not meet exclusion criteria (see exclusion criteria e) and f)).

Upon confirmation of eligibility, the study coordinators will call the pharmacy, which will be the LA BioMed Investigational Drug Service (IDS). The research pharmacists at the LABioMed Investigational Drug Service (IDS) will dispense the medication to the subject. Subjects will be given detailed verbal instructions on the use of the medication in either English or Spanish as preferred by the subject. The subject will be given a medication diary and asked to record the time of day when they take each pill as well as any side effects or comments. The subject will be given a small card to keep on their person with information about the study and study staff and emergency contact information. The study staff will answer any questions that the subject has at this time and will encourage the subject to contact the study staff with any future questions.

The subject will present to the Clinical and Translational Research Unit (CTR), the clinical site of the UCLA Clinical and Translational Science Institute (CTSI) on the Harbor-UCLA campus for follow up visits. These follow up visits will occur at week 1, week 2, week 3, week 4, week 5, week 6, week 7, week 8, week 9, week 10, week 11, week 12 and week 13. All subjects will return for follow up visits on weeks 1 – 5 and 12, and subjects still taking the study drug after week 5 will continue to return for weekly follow up visits until they complete the course or until they reach 12 weeks. Once subjects complete the course of the study drug, they will return for one additional weekly follow up visit (e.g. if a patient completes the study drug at 7 weeks, they will return for visits on weeks 1-8 and week 12). If subjects take the study drug for 12 weeks, they will return for a final follow up visit on week 13.

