At each follow up visit, CBC and CMP (comprehensive chemistry panel including liver function tests) will be collected via a blood draw. This blood sample will be sent to Quest Diagnostics by the

PROTOCOL TITLE: *Tolerability, Safety, and Efficacy of Tedizolid as Oral Treatment for Bone and Joint Infection*

Revised: 8/10/18 Version 1.6

CTSI/CTRU, an outside laboratory that is contracted with the CTSI/CTRU to process blood samples. Additionally, standardized surveys (See Data Collection Fields V 1.0, Neuropathy Scale V 1.0, attached) will be administered about drug side effects and tolerability, and adverse events will be measured using the Medical Dictionary for Regulatory Activities Terminology (MedDRA) version 18.1 (or the most current version). At these follow up visits, we will also record data points relevant to defining the efficacy of the treatment, such as the duration of the antibiotic treatment, any unplanned surgical procedures prompted by inadequate infection control, recurrence of signs or symptoms of bone and joint infection, and any other relevant comments or observations from the subject. The subject will also be asked to bring their study drug medication bottle and medication diary in order to assess compliance. If a subject suspects pregnancy during a follow up visit, they will be given a pregnancy test and the study team will track their reported menstrual cycle. If the subject does become pregnant, they will be discontinued from the study drug. Study staff will follow and collect data on the course of the pregnancy and the health of the child for at least 6-8 weeks after delivery.

Patients with evidence of myelosuppression will continue to have weekly CBCs performed until resolution of the myelosuppression.

Subjects who are concurrently taking serotonergic agents while receiving the study drug will be monitored for signs and symptoms of serotonin syndrome at each scheduled follow-up visit. Symptoms of serotonin syndrome include agitation or restlessness, confusion, rapid heartbeat and high blood pressure, dilated (big) pupils, loss of muscle coordination or twitching muscles, muscle rigidity (stiffness), heavy sweating, diarrhea, headache, shivering and goose bumps.

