The study is descriptive and thus no formal statistical analysis plan has been performed. The number of subjects chosen (n=50) is based on a sample size believed to have sufficient power to reassure clinicians that tedizolid is safe, tolerable, and efficacious for the treatment of native bone and hardware-associated bone and joint infection.

Of note, confidence intervals for safety and efficacy will be calculated. Confidence intervals for outcomes of low incidence (e.g., thrombocytopenia) will be approximately +/-3 - 7%. E.g., assuming n=50 subjects, a low incidence outcome with a probability of 2.5% will have 95% confidence intervals of <0.1%-6.8%. Outcomes with probabilities farther from 0% or 100% will have wider confidence intervals. For example, we anticipate cure rate will be 80%, in which assuming n=50, 95% confidence intervals will be 69%-91%.

Provide a power analysis.

Confidence intervals for safety and efficacy will be calculated. Confidence intervals for outcomes of low incidence (e.g., thrombocytopenia) will be approximately +/-3 - 7%. E.g., assuming n=50 subjects, a low incidence outcome with a probability of 2.5% will have 95% confidence intervals of <0.1%-6.8%. Outcomes with probabilities farther from 0% or 100% will have wider confidence intervals. For example, we anticipate cure rate will be 80%, in which assuming n=50, 95% confidence intervals will be 69%-91%.

Describe the steps that will be taken to secure the data (e.g., training, authorization of access, password protection, encryption, physical controls, certificates of confidentiality, and separation of identifiers and data) during storage, use, and transmission.

All source documents and specimens will be coded meaning these items will be labeled the subjects Study ID number and will include dates (case report forms) rather than his/her name and/or date of birth. We will maintain a separate password-protected key list/log (electronic file) linking each subject to their Study ID and a hardcopy will be maintained separate from individual subject files in a separate locked filing cabinet. Access to study computers and files will be limited to study personnel. Human research records including Informed Consent Forms

PROTOCOL TITLE: *Tolerability, Safety, and Efficacy of Tedizolid as Oral Treatment for Bone and Joint Infection*

Revised: 8/10/18 Version 1.6

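### The only population the plan names is 50 week-12 completers, with non-completers replaced, so toxicity rates reported in it would tend to be too low

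*Combined protocol and SAP*

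**What the plan says.** **Accrual and population (section 9c).** Enrolment is tied to completion: "We will enroll subjects until we obtain 50 subjects who are analyzable and have completed all follow-ups through 12 weeks". The reason given for enrolling about 55 is that "we anticipate an approximate 10% attrition rate in order to have study outcomes for 50 subjects in total". Attrition is described as uncertain, so "we may need to enroll a different number of subjects to achieve our analyzable population of 50 subjects".

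**Endpoints (sections 4 and 9f).** "The primary study endpoint is the tolerability of prolonged (≥ 4 weeks) courses of tedizolid antibiotic therapy"; safety is secondary and efficacy tertiary. Section 4 names gastrointestinal, hematologic and neurologic toxicity as the focus.

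**Analysis (section 9i).** "The study is descriptive and thus no formal statistical analysis plan has been performed". The section then explains how the sample size was set: "The number of subjects chosen (n=50) is based on a sample size believed to have sufficient power to reassure clinicians that tedizolid is safe". The worked confidence intervals, for a rare safety event and for cure, both use n=50.

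**Withdrawal (section 9l).** The principal investigator will withdraw a subject when safety requires it. Subjects may also be withdrawn for cytopenias, liver abnormalities, neuropathy symptoms or gastrointestinal intolerance. Subjects who withdraw owe no more visits. The section does not say whether that also covers withdrawal by the investigator, and apart from pregnancy it does not separate stopping the drug from leaving the study.

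**Follow-up and safety data (sections 9g and 9k).** "All subjects will return for follow up visits on weeks 1 – 5 and 12". For one toxicity, blood counts go on for longer: "Patients with evidence of myelosuppression will continue to have weekly CBCs performed until resolution of the myelosuppression". Pregnancies are followed. A phone survey three months after antibiotics end asks about adverse events. Adverse events are collected from enrolment, and the Data Safety Monitor reviews all that are reported.

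None of the text available for review defines an all-treated, safety or intention-to-treat set. Part of section 7 and the attached Data Collection Fields list were not available.

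**The concern.** The grounds for withdrawal in section 9l are largely the events that the primary and secondary endpoints are meant to count. A subject taken out of the study for one of them before week 12 would normally not complete all follow-ups, so would not be one of the 50, and another subject would be enrolled in that place. Selection into the named population would then depend on the outcome.

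This matters because the trial has one arm and is descriptive. Its product is a set of rates with intervals, intended to reassure clinicians about prolonged use. There is no comparison group in which the same selection would show, so the choice of denominator largely determines the result.

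**Working it through.** **1. The plan's own figures.** Inputs: 50 analysable subjects and 10% attrition (section 9c); n=50, an event rate of 2.5% and a cure rate of 80% (section 9i).
- Enrolment: 50 / 0.90 = 55.6, and 50 × 1.10 = 55. The stated figure of about 55 is reproduced.
- Intervals, p ± 1.96 × √(p(1−p)/50):
  - 2.5% ± 4.3 points gives −1.8% to 6.8% (stated as below 0.1% to 6.8%, so the lower limit was truncated).
  - 80% ± 11.1 points gives 68.9% to 91.1% (stated as 69%–91%).

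The arithmetic is sound, and it confirms that the planned precision uses the 50 analysable subjects rather than the roughly 55 enrolled.

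**2. Effect of the denominator.** Let m be the number of dosed non-completers, k the number of these who stopped for toxicity, and x the number of toxicity stops among the 50 completers.
- Completer rate = x/50. All-dosed rate = (x + k)/(50 + m).
- Understatement = [m/(50 + m)] × (k/m − x/50).

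The documents give neither k nor x, so both are assumptions. With m = 5 (all 55 dosed), the weight is 5/55 = 9.1%. Intervals are exact (Clopper–Pearson) 95%.

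| Completers | k of 5 | All dosed | Understatement |
|---|---|---|---|
| 0/50 = 0% (0–7.1%) | 0 | 0/55 = 0% (0–6.5%) | 0 |
| 0/50 | 1 | 1/55 = 1.8% (0.05–9.7%) | 1.8 points |
| 0/50 | 2 | 2/55 = 3.6% (0.4–12.5%) | 3.6 points |
| 0/50 | 5 (worst case) | 5/55 = 9.1% (3.0–20.0%) | 9.1 points |
| 2/50 = 4.0% (0.5–13.7%) | 0 | 2/55 = 3.6% (0.4–12.5%) | −0.4 points |
| 2/50 | 1 | 3/55 = 5.5% (1.1–15.1%) | 1.5 points |
| 2/50 | 5 (worst case) | 7/55 = 12.7% (5.3–24.5%) | 8.7 points |

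Against 0/50, the all-dosed estimate passes the completer upper limit of 7.1% only at k = 4 (4/55 = 7.3%) or k = 5. If nobody leaves because of toxicity, the completer rate is equal or slightly too high.

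**3. Other assumptions.**
- Some of the five never dosed: with two dosed, both stopping for toxicity, 2/52 = 3.8% (0.5–13.2%) against 0/50.
- Attrition of 20% (assumed; the plan says 10% but calls it unclear): 50 / 0.80 = 62.5, so 63 enrolled and 13 non-completers. Against 0/50, the all-dosed rate runs from 0/63 (0–5.7%) to a worst case of 13/63 = 20.6% (11.5–32.7%).
- Cure at the plan's 80% (40/50): 40/55 = 72.7% (59.0–83.9%) if none of the five is cured, and 45/55 = 81.8% (69.1–90.9%) if all are.

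**The case against.** The strongest reply is that section 9c is about accrual, not analysis. It answers a form question on how many subjects are needed, and it lists being analysable and having completed follow-up as two conditions, which suggests they differ. Section 9i does not restrict any rate to completers, and its n=50 only illustrates interval width. On this view the analysis set is merely undefined.

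Part of this stands. *Analyzable* has no other definition, and a reader might infer that the plan discards the data of everyone who leaves early. The documents do not support that:
- No sentence says so, and adverse events are recorded from enrolment and reach the Data Safety Monitor whether or not the subject completes.
- Withdrawal for the listed toxicities is permitted, not automatic. A subject who stops tedizolid but attends through week 12 still counts.
- The three-month call asks about adverse events and is not limited to completers, although the plan does not say whether withdrawn subjects are called.

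The accrual-only reading still fails. Section 9c itself speaks of an analysable population of 50 and of outcomes for 50 out of about 55, and section 9i uses the same number. Review by the monitor protects subjects during the trial but sets no denominator for the reported rates. That this is a pilot with no test or threshold lowers the stakes of any one figure, but in a descriptive study the rate is the finding.

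**Conclusion.** The concern holds as a tendency. Rates reported in the only named population would understate toxicity whenever non-completers had it more often than completers, and section 9l makes that the likely direction. It bears on the primary and secondary endpoints and would favour the drug.

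The size cannot be fixed from the documents. At the planned attrition, with all 55 dosed and no toxicity stops among completers, one or two toxicity withdrawals give an understatement of 1.8 to 3.6 points. That is comparable with the 2.5% event rate that section 9i uses as its example. The 9.1-point figure is a worst case in which all five non-completers stopped for toxicity; neither it nor the 20% attrition case should be read as expected. The conclusion also assumes that the material not available for review contains no all-treated definition.

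**What to change.** **Section 9c and the data analysis plan in 9i**
1. Define the tolerability and safety set as every subject who takes at least one dose, using all data to last contact.
2. Report stopping tedizolid for an adverse event in that set, with an exact 95% CI.
3. Keep week-12 completers as a sensitivity analysis.
4. Report cure in all dosed subjects, with a sensitivity analysis counting unknown outcomes as not cured.

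**Section 9l**

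5. Record the reason for each withdrawal, if the Data Collection Fields list does not already, and whether it is from study drug only or from the study.
6. State that withdrawn subjects who agree are still contacted for the week-12 survey and the three-month call.

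Items 1 to 4 restore events that were observed. They do not recover events after last contact, which is why item 6 is needed, and even then some will be missed.

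**Cost.** Protocol wording, possibly one data field, and follow-up contacts for about five subjects at the planned attrition. No extra patients are needed, and enrolment to 50 completers can stay as an accrual target. Reported rates may be less favourable, and that is the price of a denominator that does not depend on the outcome.

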No materials will be used to directly recruit patients. Flyers will be given to select Inpatient and Outpatient Clinic staff. Flyers will also be given to physicians outside Harbor UCLA Medical Center. Once the physician identifies a potential patient and receives verbal consent from the patient, the physician will call the study staff. At that point the study staff will screen the patient via phone and a waiver of written consent will be utilized for screening purposes only.

Describe the amount and timing of any payments to subjects.

The subjects will be paid in cash for their follow up visits. They will be paid \$30 for the visit on week 1, \$35 for the visit on week 2, \$40 for the visit on week 3, \$40 for the visit on week 4, \$45 for the visit on week 5, \$45 for the visit on week 6, and \$50 each visit for visits on weeks 7, 8, 9, 10, 11, 12 and 13.

The total amount of compensation will range between \$240 and \$585 based on the number of follow up visits the subject completes. All subjects will complete visits on Weeks 1,2,3,4,5, and 12. Subjects still taking the study drug at week 6 will be required to return for a Week 6 follow up visit. Subjects still taking the study drug at week 7 will be required to return for a week 7 follow up visit, and so on- while patients are receiving the study drug they will return for weekly follow up visits until they have completed the course, or until they have reached 12 weeks. Once subjects complete the course of the study drug, they will return for one additional weekly follow up visit (e.g. if a patient completes the study drug at 7 weeks, they will return for visits on weeks 1-8 and week 12). If subjects take the study drug for 12 weeks, they will return for a final follow up visit on week 13.

b) Inclusion and Exclusion Criteria*

Describe how you will screen for eligibility.

Describe the criteria that define who will be included or excluded in your final study sample.

For this investigation, we will use strict inclusion and exclusion criteria.

Inclusion criteria will include:

a) Treatment of bone and joint infection in which therapy for Gram-positive organisms is suspected or documented, as determined by the treating physician and treatment of at least 4 weeks is planned. Bone and joint infection and trauma-associated bone and joint infection will

PROTOCOL TITLE: *Tolerability, Safety, and Efficacy of Tedizolid as Oral Treatment for Bone and Joint Infection*

Revised: 8/10/18 Version 1.6

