Additionally, subjects may be withdrawn in the following circumstances development of significant cytopenias and liver function abnormalities, symptoms of neuropathy, gastrointestinal intolerance, or, in the opinion of the investigator, any new severe signs or symptoms that may be related to the study drug.

PROTOCOL TITLE: *Tolerability, Safety, and Efficacy of Tedizolid as Oral Treatment for Bone and Joint Infection*

Revised: 8/10/18 Version 1.6

If a subject becomes pregnant during the study, they will be discontinued from the study drug. Study staff will follow and collect data on the course of the pregnancy and the health of the child for at least 6-8 weeks after delivery.

Describe any procedures for orderly termination.

Termination of the study will occur based on the primary investigators judgment. Subjects will be provided referrals for their medical conditions, if needed.

Describe procedures that will be followed when subjects withdraw from the research, including partial withdrawal from procedures with continued data collection.

Subjects who withdraw from the study will be asked to notify the study team. No further visits will be required. Additionally, if a subject withdraws from the study, a member of the study team will contact their primary treatment physician and/or infectious disease consultant to ensure that the patient is given antibiotic therapy immediately upon discontinuation of study drug.

10) Risks to Subjects*

List the reasonably foreseeable risks, discomforts, hazards, or inconveniences to the subjects related the subjects' participation in the research. Include as may be useful for the HSC's consideration, describe the probability, magnitude, duration, and reversibility of the risks. Consider physical, psychological, social, legal, and economic risks.

According to the package insert for tedizolid (Sivextro), adverse reactions were evaluated for 1050 patients treated with tedizolid (200 mg oral/intravenous once daily for 6 days) in two Phase 2 and two Phase 3 ABSSSI (acute bacterial skin and soft structure infection) clinical trials. The median age of patients treated with tedizolid (200 mg oral/intravenous once daily for 6 days) in the Phase 2 and Phase 3 ABSSSI trials was 42 years, ranging between 17 and 86 years old. Patients treated with tedizolid (200 mg oral/intravenous once daily for 6 days) were predominantly male (65%) and white (82%).

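### The analyzable population is built from 12-week completers with no all-dosed set, so the tolerability and safety rates may leave out subjects withdrawn for toxicity

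*Combined protocol and SAP*

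**What the plan says.** Section 9) c), Local Number of Subjects, sets the rule for ending enrolment: "We will enroll subjects until we obtain 50 subjects who are analyzable and have completed all follow-ups through 12 weeks". It assumes about 10% attrition and plans roughly 55 enrolments "in order to have study outcomes for 50 subjects in total". It then adds that "we may need to enroll a different number of subjects to achieve our analyzable population of 50 subjects". Enrolment therefore stays open until the completer count is reached.

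Section 9) f) makes tolerability the primary endpoint and safety the secondary. Section 9) i) says the study is descriptive, with no formal statistical analysis plan. Its example intervals also take 50 as the denominator ("assuming n=50 subjects, a low incidence outcome with a probability of 2.5" percent). No section defines a safety, all-dosed or intention-to-treat set.

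Section 9) l), Withdrawal of Subjects, gives the grounds: "subjects may be withdrawn in the following circumstances development of significant cytopenias and liver function abnormalities, symptoms of neuropathy, gastrointestinal intolerance". For subjects who withdraw, "No further visits will be required", and the study team ensures that the patient "is given antibiotic therapy immediately upon discontinuation of study drug". The payment and visit text in section 9) a) says "All subjects will complete visits on Weeks 1,2,3,4,5, and 12".

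**The concern.** The permitted grounds for withdrawal largely coincide with what section 4) names as the study's focus: gastrointestinal tolerability, hematologic toxicity and neurologic toxicity. Loss from the analyzable population is therefore likely to be related to the outcome. Intolerance bad enough to end participation is the clearest failure of a tolerability endpoint, yet a subject removed for it before week 12 has not completed follow-up and does not belong to the 50 as described.

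There is no control arm, so no comparison rate would expose the selection. The observed rate is the whole result, and section 9) i) justifies the sample size by the reassurance it should give clinicians about safety and tolerability. A completer-based rate understates withdrawal for toxicity. It also understates any toxicity that is more frequent among those lost than among completers, which is what one would expect for uncommon events such as cytopenia or neuropathy.

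A second, smaller gap is follow-up after withdrawal. Section 9) g) continues weekly CBCs until myelosuppression resolves, but nothing equivalent is stated for neuropathy, liver abnormality or gastrointestinal toxicity.

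**Working it through.** **The plan's own figures**

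- Enrolment: 50/(1 − 0.10) = 55.6, against about 55 stated (50 × 1.10 = 55). This agrees within rounding.
- Intervals at n = 50, from p ± 1.96·√(p(1 − p)/50): for p = 2.5%, −1.8% to 6.8%; for p = 80%, 68.9% to 91.1%. These match the protocol's limits, except that the negative lower limit appears there as less than 0.1%. The arithmetic reproduces; the question is which subjects make up the n.

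**Assumptions for the size of the effect**

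55 enrolled and all dosed, 50 complete, 5 lost. The number of the 5 lost to toxicity is not in the protocol, so a range from none to all is shown. Intervals are exact (Clopper-Pearson) 95%.

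*Rate of withdrawal for toxicity*

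| Withdrawn for toxicity | All dosed | 12-week completers |
|---|---|---|
| 0 | 0/55 = 0% (0–6.5%) | 0/50 (0–7.1%) |
| 1 | 1/55 = 1.8% (0.0–9.7%) | 0/50 (0–7.1%) |
| 3 | 3/55 = 5.5% (1.1–15.1%) | 0/50 (0–7.1%) |
| 5 | 5/55 = 9.1% (3.0–20.0%) | 0/50 (0–7.1%) |

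The completer column is zero whatever happens, because nobody withdrawn before week 12 can be in it.

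*One uncommon toxicity, seen in 1 completer*

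- Completers: 1/50 = 2.0% (0.1–10.6%).
- All dosed, 1 of the 5 lost affected: 2/55 = 3.6% (0.4–12.5%).
- All dosed, 3 of the 5 lost affected: 4/55 = 7.3% (2.0–17.6%).

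**Direction of the bias**

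With x affected completers and k affected among the 5 lost, the completer rate is too low only if x/50 < (x + k)/55. That reduces to x/50 < k/5.

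- k = 1: equal at x = 10 (10/50 = 11/55 = 20.0%); reversed from x = 11 (11/50 = 22.0% against 12/55 = 21.8%).
- k = 2: equal at x = 20 (20/50 = 22/55 = 40.0%); reversed from x = 21 (21/50 = 42.0% against 23/55 = 41.8%).

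So an uncommon toxicity is understated once even one of those lost had it, while a common symptom may be unaffected or slightly overstated.

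**The case against.** The best reply is that the protocol never says the rates will be computed in completers only. Section 9) c) answers a question about accrual, the term analyzable is not defined, and the n = 50 intervals are planning examples. On that reading, 50 completers is only a rule for stopping enrolment.

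The withdrawal text is also softer than it first looks. Withdrawal for toxicity is permitted, not required. The release from visits follows a sentence asking subjects to notify the team, which fits withdrawal by the subject better than removal by the investigator. Someone who stops tedizolid but stays in the study is still due at weeks 1–5 and 12 and can be one of the 50. Adverse events up to withdrawal are recorded and reviewed monthly and quarterly (section 9) k)), so the data for an all-dosed rate up to that point would exist. Finally, this is a descriptive pilot, the toxicity share of attrition is assumed, and the intervals overlap widely.

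Most of this stands, and it narrows the point to subjects withdrawn from the study itself. It does not remove it. Section 9) c) attaches both the analyzable population and the study outcomes to the same 50 subjects, and no other text overrides that. The sentence after the release from visits links withdrawal to stopping the drug. Safety monitoring does not set the numerator or denominator of the reported rates.

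**Conclusion.** The concern holds. Followed as written, the plan can report tolerability and safety in a group from which subjects withdrawn for toxicity have been removed and replaced. That exclusion is inferred from the population definition and the withdrawal rules, so the claim is that the rates may be understated, not that they will be.

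The size is illustrative. It rests on 55 dosed, 5 lost, and an assumed toxicity share that includes zero, in which case there is no understatement. Within that range, a withdrawal rate of up to 9.1% would not appear at all, and an uncommon toxicity reported at 2.0% could be 3.6% to 7.3% among all dosed in the cases shown. Because the primary endpoint is affected and the correction is a few sentences, it should be made.

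**What to change.** - **Section 9) c):** keep 50 completers as the accrual target, and define the tolerability and safety population as every subject who takes at least one dose of tedizolid.
- **Section 9) i):** report each toxicity, and the proportion stopping tedizolid for an adverse event or laboratory abnormality, in all dosed subjects with exact 95% CIs. List withdrawals by reason.
- **Section 9) l):** separate stopping the drug from leaving the study, as the protocol already does for pregnancy. Unless consent is withdrawn, ask subjects who stop for toxicity to attend the remaining core visits (weeks 1–5 and 12) and take the 3-month call.

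**Cost.** No extra subjects. A subject who stops in week 1 and attends weeks 2–5 and 12 is paid 35 + 40 + 40 + 45 + 50 = $210, or $1,050 for five such subjects, plus laboratory tests, which are not priced here. This lies within the protocol's per-subject minimum of $240, which is exactly the sum for weeks 1–5 and 12 (30 + 35 + 40 + 40 + 45 + 50). The downsides are that reported rates may look less favourable and that some withdrawn subjects will decline visits.
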